‡ Analysis 1 will be performed on all data collected up to Day 91 for at least primary and secondary endpoints based on both study parts (except for cell-mediated immune response at pre-Dose 2 [Day 61] in Part A and Part B and the occurrence of RSV RTI in Part B). Analysis 2 will be performed when all safety data up to Month 8 (Visit 7) are available. The analyses will be based on data as clean as possible.

- **Experimental design:** Phase I/II, observer-blind, randomized, controlled, multi-country study with 2 parts (i.e., Part A in young adults aged 18-40 years with 4 parallel groups and Part B in older adults aged 60-80 years with 10 parallel groups).
- **Primary Completion Date (PCD):** last visit of the vaccination phase in Part B (Visit 6 [Day 91]).
- **End of Study (EoS):** Last testing results released of samples collected up to Visit 8 in Part B (Month 14) (for assays related to primary and secondary endpoints only).
- **Treatment allocation:** Subjects will be randomized using a centralised randomization system on internet (Sbir) on Day 1.

In Part A, the aim is to enrol approximately 48 subjects (~12 per group) aged 18-40 years. The randomization algorithm will use a minimisation procedure accounting for center and gender.

In Part B, the aim is to enrol approximately 700 subjects (~70 per group) aged 60-69 years and approximately 300 subjects (~30 per group) aged 70-80 years. The randomization algorithm will use a minimisation procedure accounting for age, center and gender in each step.

- **Study groups:**

For the investigational RSV vaccines in Part A and Step 1 in Part B, the RSVPreF3 high-dose formulation containing 120 µg RSVPreF3 will be used to prepare the vaccines for all dose groups (i.e., 30 µg, 60 µg and 120 µg dose groups). For Step 2 in Part B, the RSVPreF3 low-dose and mid-dose formulations (containing 30 µg and 60 µg RSVPreF3, respectively) will be used for the groups receiving 30 µg and 60 µg of RSVPreF3, respectively, and the RSVPreF3 high-dose formulation will be used for the 120 µg dose groups. As the reconstitution methods for the vaccines

CONFIDENTIAL208851 (RSV OA=ADJ-002)
Statistical Analysis Plan Amendment 2

administered to subjects enrolled in Step 1 and 2 of Part B will be different, separate study groups have been identified (referred to as B1 and B2). Throughout this document, the combined groups for Steps 1 and 2 are mentioned when referring to the number of groups in Part B (10 groups).

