 - **Part A:** Approximately 48 young adults aged 18-40 years will be enrolled and vaccinated with the first dose. If the IDMC evaluation on data up to 30 days post Dose 1 is favorable, the Part A study participants will be vaccinated with the second dose and Part B of the study will be initiated.

CONFIDENTIAL

208851 (RSV OA=ADJ-002)
Statistical Analysis Plan Amendment 2

- **Part B:** This part will be conducted in a 2-step staggered design to ensure maximum safety of the participating subjects. In Step 1, approximately 100 subjects will be enrolled and vaccinated. Safety evaluations based on unblinded data from those first 100 subjects will be performed by the IDMC to allow the start of Step 2. In Step 2, the remaining study participants (N \geq 900) will be recruited and vaccinated.

In total, 6 IDMC meetings for safety evaluation are foreseen in the vaccination phase of the study (Epoch 002), i.e., 2 meetings in Part A and 4 meetings in Part B.

During the persistence phase of Part B (Epoch 003), 2 IDMC meetings will be planned with an interval of approximately 6 months.

If any safety concern is identified by the investigator or the sponsor, *ad-hoc* safety evaluations by the IDMC may be performed.

Analysis planned for IDMC evaluations are described in a separate document (SAP for IDMC).

- **Group description for analysis:**

For analysis based on subjects in Part A and Part B Step 1 (B1), the group labels listed in table below will be used in the TFLs.

For final analysis based on subjects from Part B Steps 1 and 2, the groups will be pooled (B1 and B2) and the Pooled group labels will be used in the TFLs.

Table 1 Groups description

Group label in tables	Group definition for footnote	Pooled Group label in tables	Pooled Group definition for footnote
30-PLAIN_A	subjects receiving unadjuvanted 30 mcg RSVPreF3 in Part A	NA	
60-PLAIN_A	subjects receiving unadjuvanted 60 mcg RSVPreF3 in Part A	NA	
120-PLAIN_A	subjects receiving unadjuvanted 120 mcg RSVPreF3 in Part A	NA	
Placebo_A	subjects receiving Placebo in Part A	NA	
30-PLAIN_B1	subjects receiving unadjuvanted 30 mcg RSVPreF3 in Part B Step 1	30-PLAIN_B	subjects receiving unadjuvanted 30 mcg RSVPreF3 in Part B
30-PLAIN_B2	subjects receiving unadjuvanted 30 mcg RSVPreF3 in Part B Step 2	30-PLAIN_B	subjects receiving unadjuvanted 30 mcg RSVPreF3 in Part B

CONFIDENTIAL208851 (RSV OA=ADJ-002)
Statistical Analysis Plan Amendment 2

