5.3.2.3. Between groups analysis

Statistical comparisons will be performed on the logarithm base 10 transformed results, in terms of RSV-A neutralizing antibody titers and frequency of RSVPreF3-specific CD4+ T-cells expressing at least 2 markers among IL-2, CD40L, TNF- α , IFN- γ .

a. Comparisons versus Placebo:

The 9 RSV formulations will be compared to the Placebo (control group) at Day 31 and Day 91 using an ANCOVA model with the Dunnett's adjustment method for multiplicity. The model will include the treatment group and the age category (age at Dose 1: 60-69 or 70-80 years) as fixed effects, and the pre-vaccination log10-transformed titer as covariate. Geometric mean ratios between groups and associated Dunnett's adjusted 95% CIs of the ratios will be tabulated.

The Dunnett's test is specifically designed for situations where all groups are to be compared against one "Reference" group. It is commonly used after ANCOVA has rejected the hypothesis of equality of the means of the distributions.

Here is an example of SAS code that will be used:

```
PROC MIXED DATA=test (where=(visit=D91));
  CLASS treatmnt Adj agecat;
  MODEL log(titer)=treatmnt baseline agecat / ddfm=KR DDFM=KR
  outpm=pred_model cl;
  REPEATED / group=Adj ; /* test homogeneity of variances and consider
  different variance by adjuvant content if appropriate */
  LSMEANS treatmnt / ALPHA=0.05 Adjust=Dunnett pdiff=control ("Placebo")
  CL;
RUN;
```

CONFIDENTIAL208851 (RSV OA=ADJ-002)
Statistical Analysis Plan Amendment 2**b. Comparisons between RSV groups:**

The difference between RSV groups will be evaluated using an ANCOVA model including the adjuvant content (AS01B, AS01E, Plain), the antigen dose (30, 60, 120 µg), the visit (Day 31, Day 91) and the age category (age at Dose 1: 60-69 or 70-80 years) as fixed effects, and the pre-vaccination log10-transformed titer as covariate. The adjuvant by antigen interaction will also be tested, and included in the model if significant at 10% (p-value <10%).

Based on this global model, appropriate contrasts will be used to perform the following comparisons:

1. Effect of the second vaccination:

The means one month post-Dose 2 (Day 91) and one month post-Dose 1 (Day 31) will be compared within each pooled group according to adjuvant content (AS01B, AS01E and Plain) (One-sided alpha=2.5% for each superiority test: 2 doses > 1 dose). Geometric mean ratios and associated 95% CIs will be tabulated.

2. Adjuvant effect:

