		Group 1	N	GM<T,F>	95% CI	Group 2	N	GM<T,F>	95% CI	Value	LL	UL	
Assay	Timepoint	Group 1	N	GM<T,F>	LL	UL	Group 2	N	GM<T,F>	LL	UL	p-value	
<assay name>	<each timing>	AS01B_B					PLAIN_B						
		AS01E_B					PLAIN_B						
		AS01B_B					AS01E_B						

Short group label = long group label

GM<T,F> = geometric mean antibody <titer, frequency> adjusted for covariates (ANCOVA model)

N = Number of subjects with both pre- and post-vaccination results available

95% CI = 95% confidence interval for the adjusted GMT (Ancova model: adjustment for covariates - pooled variance);

LL = lower limit, UL = upper limit

ANCOVA model on the log-transformed <titers, frequencies> with the pre-vaccination log-transformed

<titer,frequency> as covariate, and adjuvant content, antigen dose and age category as fixed effects

Group 1 is considered superior to Group 2 if one-sided p-value <0.025

CONFIDENTIAL

208851 (RSV OA=ADJ-002)
 Statistical Analysis Plan Amendment 2

Template Table 30 Comparisons of the RSV groups (by antigen dose level) in terms of <RSV A Neutralizing antibody titers, RSVPreF3-specific CD4 T cells expressing at least 2 markers among IL-2, CD40L, TNFa, IFNg> at Day 91 (ANCOVA model) – Part B <Per Protocol set >

		Group 1					Group 2					GM<T,F> ratio (Group 1 / Group 2)			
					95% CI					95% CI			95% CI		95% CI
Assay	Timepoint	Group 1	N	GM<T,F>	LL	UL	Group 2	N	GM<T,F>	LL	UL	Value	LL	UL	p-value
<assay name>	<each timing>	120-PLAIN_B					60-PLAIN_B								
		120-PLAIN_B					30-PLAIN_B								
		60-PLAIN_B					30-PLAIN_B								
		120-AS01E_B					60-AS01E_B								
		120-AS01E_B					30-AS01E_B								
		60-AS01E_B					30-AS01E_B								
		120-AS01B_B					60-AS01B_B								
		120-AS01B_B					30-AS01B_B								
		60-AS01B_B					30-AS01B_B								

Short group label = long group label

GM<T,F> = geometric mean antibody <titer, frequency> adjusted for covariates (ANCOVA model)

N = Number of subjects with both pre- and post-vaccination results available

95% CI = 95% confidence interval for the adjusted GMT (Ancova model: adjustment for covariates - pooled variance);

LL = lower limit, UL = upper limit

ANCOVA model on the log-transformed <titers, frequencies> with the pre-vaccination log-transformed <titer,frequency> as covariate, and the treatment, age category and gender as fixed effects

Group 1 is considered superior to Group 2 if one-sided p-value <0.025

CONFIDENTIAL208851 (RSV OA=ADJ-002)

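### Part B is minimised on age, center and gender within step, but of these the between-group ANCOVAs carry only age category, and the Template Table 30 footnote names a different model

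*SAP*

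**What the plan says.** **Allocation.** SAP section 2 states for Part B: "The randomization algorithm will use a minimisation procedure accounting for age, center and gender in each step". The target is "approximately 700 subjects (~70 per group) aged 60-69 years and approximately 300 subjects (~30 per group) aged 70-80 years", so about 100 per group across ten groups. On the staging: "In Step 1, approximately 100 subjects will be enrolled and vaccinated"; the remaining 900 or more follow in Step 2.

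**Models in the text and code.**
- *Versus placebo (5.3.2.3 a):* "The model will include the treatment group and the age category (age at Dose 1: 60-69 or 70-80 years) as fixed effects", plus the pre-vaccination log10 titer. The code agrees: "MODEL log(titer)=treatmnt baseline agecat / ddfm=KR DDFM=KR".
- *Between RSV formulations (5.3.2.3 b):* adjuvant content, antigen dose, "the visit (Day 31, Day 91) and the age category (age at Dose 1: 60-69 or 70-80 years) as fixed effects", plus the pre-vaccination log10 titer. The code adds interactions but no center, gender or step. The section takes its comparisons, including the pairwise dose ratios, from this one global model.
- *CD4 model (5.3.2.3):* the same factors, with pre-vaccination induction frequency and post-vaccination background frequency as covariates. It too has no center, gender or step.

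**Templates (12.3.2).** The model footnotes of Template Tables 27, 28, 29 and 31 contain no gender. The footnote of Template Table 30, which shows the dose ratios, gives the pre-vaccination value "and the treatment, age category and gender as fixed effects".

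**The concern.** When allocation is forced to balance on a factor that predicts the response, part of that factor's variance is removed from the treatment differences. A model without the factor leaves that variance in the residual. Its standard errors then describe a noisier comparison than the one actually made, so intervals are too long and tests too cautious. The SAP keeps one of the three minimisation factors and gives no reason for dropping the other two, or the step within which minimisation runs.

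The Template Table 30 footnote is a separate defect. Two models are written down for the same dose ratios. A programmer could follow either and claim to follow the plan, and the dose ratios could be adjusted for gender while the adjuvant ratios are not.

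What is at stake is modest precision on the adjuvant, dose and placebo ratios, and an unambiguous model for the dose comparison. Section 5.3.1.3 uses one-sided 2.5% tests for the adjuvant effect and for superiority of 120 µg or 60 µg, so these results are meant to carry weight in comparing formulations.

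**Working it through.** **No figure to reproduce.** The SAP gives no SD, effect size or power for these comparisons, and no prognostic strength for center, gender or step. The share of residual variance they explain after baseline and age, R², is therefore an assumption, shown as a range.

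**1. Allocation against models**

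| Factor | Used in allocation | Placebo ANCOVA | RSV-group ANCOVA | CD4 model | Template 30 footnote |
|---|---|---|---|---|---|
| Age category | yes | yes | yes | yes | yes |
| Gender | yes | no | no | no | **yes** |
| Center | yes | no | no | no | no |
| Step | stratum for minimisation | no | no | no | no |

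**2. Size of the precision loss**

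- Reported SE over adjusted SE = 1/√(1 − R²)
- Equivalent extra sample = 1/(1 − R²) − 1
- One-sided error under perfect balance = 1 − Φ(1.96/√(1 − R²))
- Power, for an effect with 80% power under adjustment = Φ(1.96 + 0.84 − 1.96/√(1 − R²))

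| Assumed R² | SE wider by | Extra sample | One-sided error | Power |
|---|---|---|---|---|
| 0 | 0% | 0% | 2.50% | 80.0% |
| 2% | 1.0% | 2.0% | 2.39% | 79.4% |
| 5% | 2.6% | 5.3% | 2.22% | 78.5% |
| 10% | 5.4% | 11.1% | 1.94% | 76.9% |

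Example at R² = 10%: 1/√0.90 = 1.054, and 1.96 × 1.054 = 2.066, whose upper tail is 1.94%.

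The error and power columns are per comparison at the 1.96 critical value. They do not carry over to the Dunnett tests in 5.3.2.3 a, which use a different critical value.

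**3. Check on the perfect-balance assumption.** Minimisation was simulated with 10 arms, 100 + 900 subjects in two steps, an assumed 20 centers, an assumed 90% biased coin and 400 trials per scenario. SE ratios were 1.025 at R² = 5% and 1.054 at 10%, matching the formula. The unadjusted model SE exceeded the actual sampling SD by less: about 2% and 4%. That corresponds to one-sided errors of about 2.3% and 2.1%. The error rates in the table are therefore the furthest the nominal 2.5% would fall.

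**4. Template Table 30 against 5.3.2.3 b.** The footnote differs in two ways: it adds gender, and it has one treatment factor in place of adjuvant content and antigen dose. Among the nine RSV groups, a single treatment factor gives the same mean structure as adjuvant, dose and their interaction. It differs when the interaction is left out, which the text requires unless its p-value is below 10%. The footnote also omits visit, but so do the footnotes of Templates 28, 29 and 31, so that omission is not peculiar to Template 30.

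**The case against.** **The loss may be nil.** This stands as a limit on the claim. A reader might infer that the standard errors *are* too wide. The SAP does not support that: it depends on center or gender being prognostic after the covariates already fitted. The pre-vaccination titer, and for CD4 the pre-vaccination and background frequencies, may absorb much of any such effect.

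**The error is conservative and the comparisons are exploratory.** This also stands. Section 6 calls all comparisons exploratory, and the primary objective is safety. It lowers the weight of the point but does not remove it, because section 5.3.1.3 still uses these tests to compare adjuvants and doses. The test that chooses Day 91 or Day 31 is less affected: it is a within-subject contrast, in which factors constant over visits largely cancel.

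**Template footnotes are illustrative.** Section 12 says they will be adapted, and the SAS example produces the dose means from a model without gender. Template 30 is therefore probably a stray footnote rather than a planned second analysis. But section 12 exempts only editorial or minor changes from amendment, and a covariate list is neither.

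**Adjusted means across templates.** A reader might also infer that adjusted means in Template 30 would disagree with those in Templates 28 and 29. Template 28 shows only Day 91/Day 31 ratios, and Template 29 shows adjuvant-pooled means, so no cell is common to both. The supported statement is that dose and adjuvant ratios would come from differently adjusted models.

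**Step as a remedy for pooling.** Of the reconstitution methods in Part B, section 2 says that those "administered to subjects enrolled in Step 1 and 2 of Part B will be different, separate study groups have been identified". It is tempting to conclude that a step term would deal with pooling B1 and B2. It would not. The formulation changes between steps for the 30 µg and 60 µg groups but not for 120 µg, and a common step effect cannot capture a dose-specific difference. The pooling itself is pre-specified.

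**Conclusion.** Two points hold.

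1. Of the factors that structure the Part B allocation, the between-group ANCOVAs in text, code and the CD4 model carry only age category. The consequence is conditional. The 1.0% to 5.4% wider standard errors rest on an assumed R² of 2% to 10%, and at R² = 0 there is no loss. The fall in one-sided error to about 2.4% to 1.9% further assumes perfect balance and applies per comparison before Dunnett. There is no type I error inflation, and nothing here makes the planned tests invalid.
2. The Template Table 30 footnote contradicts section 5.3.2.3 b. This is certain from the document and needs no assumption. Neither section 5.3 nor section 8 explains the gender term.

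The change is worth making because it is cheap and settles which model applies, not because a large loss has been shown.

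**What to change.** - In section 5.3.2.3, add to every between-group ANCOVA, humoral and CD4: gender; center, as a random effect or as fixed with small centers pooled; and step (B1/B2), as the stratum within which minimisation was run.
- State that step is there for the allocation structure only. It does not address a dose-specific formulation difference between B1 and B2.
- Use one covariate list in the text, both SAS examples, the CD4 model and the footnotes of Template Tables 27-31. Correct Template 30 so that its dose ratios come from the global model.
- Code gender and step by the section 10.1.5.2 rule for two-level covariates. Put in CLASS, step would by default be weighted equally in the least-squares means although Step 1 is only about 100 of 1,000 subjects. The CD4 ratios depend on the level of those means.

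**Cost.** SAP wording and variables that already exist. The models use about 1,000 subjects versus placebo (10 × 100) and about 900 among RSV groups (9 × 100), so a few degrees of freedom are negligible. The SAP does not give the number of centers, so the choice between random and pooled-fixed should be made with that count in hand and fixed before the models are run.

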The adjuvant effect will be tested sequentially as follow (One-sided alpha=2.5% for each superiority test):

- i. AS01B versus Plain
- ii. AS01E versus Plain
- iii. AS01B versus AS01E.

Geometric mean ratios and their 95% CIs will be computed for each comparison.

The same comparisons will also be performed by age category.

3. Antigen dose-response: test linear and quadratic effect of the antigen dose.

Depending on significance of those 2 effects, ANCOVA t-tests might be done to demonstrate superiority of 120 µg or 60 µg.

Geometric mean ratios and their 95% CIs will be computed for each pairwise comparison within each adjuvant content family (120 µg vs 60 µg, 120 µg vs 30 µg, 60 µg vs 30 µg for Plain, AS01E and AS01B groups).

Here is an example of SAS code that will be used:

```

PROC MIXED DATA=test;
  class Adj(1B, 1E, PL) Ag(30, 60, 120) visit(PD1, PD2) subject agecat;
  model log(titer) = Adj Ag visit Adj*Ag Adj*visit Ag*visit Adj*Ag*visit
  baseline baseline*visit agecat / DDFM=KR S outpm=pred_model cl;
  REPEATED visit / SUBJECT=subject type=unr group=Adj;
  /* test homogeneity of variances and consider different variance by
  adjuvant content if appropriate */

  LSMEANS Adj*visit /E slice=visit CL PDIFF ALPHA=0.05; /*option E to see
  coefficients assigned to each effect */
  LSMEANS Adj*visit /E slice=Adj CL PDIFF ALPHA=0.05;
  LSMEANS Adj*Ag*visit / slice=visit CL PDIFF ALPHA=0.05;

  /* contrasts to be added for each comparison of interest */
  QUIT;

```

CONFIDENTIAL208851 (RSV OA=ADJ-002)
Statistical Analysis Plan Amendment 2

The inferential analysis on the RSVPreF3-specific CD4+ T cells will be performed on the log-transformation frequency of the CD4+ T cells expressing at least 2 markers (background or induction) computed by adding an offset of 0.5 cells to the number of activated CD4+ T cells (Delta method, see below). These transformations are deemed appropriate for further inferential analyses provided the incidence of activated CD4+ T-cells is below 4%.

Considering:

$$X_{ijk} = \log\left(\frac{n_{Background}^{2+} + 0.5}{N_{Background}^{CD4}}\right), \text{ the log background frequency, and}$$

$$Y_{ijk} = \log\left(\frac{n_{Induction}^{2+} + 0.5}{N_{Induction}^{CD4}}\right), \text{ the log induction frequency}$$

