As described for humoral response, the differences between RSV groups will be evaluated using an ANCOVA model including the adjuvant content (AS01B, AS01E, Plain), the antigen dose (30, 60, 120 µg), the visit (Day 31, Day 91) and the age category (age at Dose 1: 60-69 or 70-80 years) as fixed effects, and the pre-vaccination log-transformed CD4 T cell frequency following induction and the post-vaccination log-transformed CD4 T cell frequency under background condition as covariates.

All interactions will also be tested and included in the model if significant.

The following model will be used to analyse the log-transformed ratio between induction and background frequencies, and provide estimates of the RSVPreF3-specific CD4+ T cell frequency relative to background frequency. *These estimates better represent the net effect of the vaccines over the CD4+ T cells frequency as the nuisance background frequency is subtracted from the induction frequency.*

$$Y_{ijk} - x_{ijk} = \mu_{jk} + \alpha_j \cdot y_{i0k} + \beta \cdot x_{ijk} + \varepsilon_{ijk}, \text{ with}$$

$$\hat{Y}_{jk} - x_{ijk} \Big|_{\bar{y}_0, \bar{x}} = \mu_{jk} + \alpha_j \cdot \bar{y}_0 + \beta \cdot \bar{x},$$

LS means conditional to \bar{y}_0 and \bar{x} , where:

i, j, k =subject i , visit j , group k ; \bar{y}_0 = mean log induction frequency at pre-vaccination,

\bar{x} = mean log background after vaccination.

Note: This analysis is assuming that the background is the same for all groups and all timepoints. This assumption will be checked during the analysis.

CONFIDENTIAL208851 (RSV OA=ADJ-002)
Statistical Analysis Plan Amendment 2

From that model, the least-squares means are then back-transformed into geometric means for the Induction / Background frequency ratio. The Background mean is then subtracted from the Induction mean and the fold-increase on that difference is calculated, as follows:

$$\hat{Z}_{jk} = 10^{\hat{Y}_{jk}} - 1 = \frac{10^{\hat{Y}_{jk}} - 10^{\bar{x}}}{10^{\bar{x}}}, \text{ and}$$

$$\text{Log}(\hat{W}_{jk}) = \text{Log}\left(\frac{\hat{Z}_{jk_2}}{\hat{Z}_{jk_1}}\right) = \text{Log}\left(\frac{10^{\hat{Y}_{jk_2}} - 10^{\bar{x}}}{10^{\hat{Y}_{jk_1}} - 10^{\bar{x}}}\right), \text{ where}$$

\hat{Z}_{jk} = mean increase from background to induction frequency relative to background frequency at visit j for treatment k , and

\hat{W}_{jk} = vaccine effect on the antigen specific frequency following adjustment for background frequency.

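### Section 5.3.2.3.b specifies two incompatible models for comparing the RSV groups; if the text is followed for RSV-A titers, the three within-adjuvant second-dose tests become one test.

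*SAP*

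**What the plan says.** SAP Amendment 2, section 5.3.2.3.b, introduces the model in words: "The difference between RSV groups will be evaluated using an ANCOVA model including the adjuvant content (AS01B, AS01E, Plain), the antigen dose", followed by visit and age category as fixed effects and the pre-vaccination log10 titer as covariate. It then adds: "The adjuvant by antigen interaction will also be tested, and included in the model if significant at 10% (p-value <10"%. No other interaction is named for the titers.

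The comparisons are drawn from that model: "Based on this global model, appropriate contrasts will be used to perform the following comparisons". Two of them are specific to adjuvant:
- Second dose: the Day 91 and Day 31 means "will be compared within each pooled group according to adjuvant content (AS01B, AS01E and Plain"), each tested one-sided at 2.5%.
- Antigen dose: "Geometric mean ratios and their 95% CIs will be computed for each pairwise comparison within each adjuvant content family", that is, three dose pairs in each of three families.

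The code is introduced with "Here is an example of SAS code that will be used". Its model statement begins "model log(titer) = Adj Ag visit Adj*Ag Adj*visit Ag*visit Adj*Ag*visit" and continues with baseline, baseline by visit and age category. Nothing in it is conditional.

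For the CD4+ T-cell response the same section says: "All interactions will also be tested and included in the model if significant". It gives no significance level. The equation below that text has a separate mean for each visit and group (mu_jk).

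Section 5.3.1.3 makes the second-dose result decide whether the later comparisons use Day 91 or Day 31.

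**The concern.** The text and the code are different models, and no sentence says which one governs. They cannot both hold, because an adjuvant-by-antigen term kept only when p<10% is not one that is always fitted.

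The difference bears on the questions asked. Whether a second dose adds anything for each adjuvant is an adjuvant-by-visit question. How antigen dose acts within each family is an adjuvant-by-antigen question. The text model omits the first term and may drop the second. Two programmers, one following the text and one the code, could report different ratios, intervals and conclusions, and could carry different days into the later steps.

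**Working it through.** **Text model, second dose.** On the log10 scale the expected titer is

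E(y) = mu + Adj(a) + Ag(g) + Visit(v) + baseline and age terms.

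The Day 91 minus Day 31 contrast within adjuvant a is Visit(91) − Visit(31). It does not depend on a. Adding Adj*Ag does not change this, because that term cancels between visits. Letting the variance differ by adjuvant, as the code allows, does not change the mean model either. The three planned tests are then one test.

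**Text model, antigen dose.** Without Adj*Ag, the 120 versus 30 µg contrast is Ag(120) − Ag(30) in every family, so 3 × 3 = 9 ratios reduce to 3 values. With Adj*Ag kept (p<10%), the families separate.

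**Code model.** Adj*visit, Adj*Ag, Ag*visit and Adj*Ag*visit are all present, so neither set is forced equal.

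**Numerical check.** One data set was simulated with about 100 subjects per RSV group (section 2 of the SAP: about 70 + about 30). The effects were assumed: true D91/D31 ratios 0.89, 1.12, 1.32 and true 120/30 ratios 1.58, 1.12, 1.00 (Plain, AS01E, AS01B).

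| Model fitted | D91/D31: Plain, AS01E, AS01B | 120/30: Plain, AS01E, AS01B |
|---|---|---|
| Text, no interaction | 1.105, 1.105, 1.105 | 1.166, 1.166, 1.166 |
| Text, Adj*Ag kept | 1.105, 1.105, 1.105 | 1.60, 1.14, 0.87 |
| Code, full factorial | 0.90, 1.14, 1.31 | 1.60, 1.14, 0.87 |

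**Size for the second dose (assumed inputs).** Take true log10 changes of 0, 0.10 and 0.10, that is, ratios 1.00, 1.26 and 1.26, and 270 subjects per pool (3 × 90). The text model estimates the mean, (0 + 0.10 + 0.10)/3 = 0.067, a ratio of 10^0.067 = 1.17 for all three. Its standard error is SD/√810. With SD of change 0.25 this is 0.0088, z = 7.6, so a second-dose benefit is claimed in Plain almost always. With SD 0.50 it is 0.0176, z = 3.8, and the claim is made about 97% of the time.

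**Size for the antigen dose (assumed inputs).** Take 90 per cell, residual SD 0.35 log10, no dose effect in Plain, and 0.10 to 0.20 log10 (120 versus 30 µg) in both adjuvanted families with 60 µg halfway. The 10% interaction test is significant in about 31% to 80% of runs. The false one-sided 2.5% claim of 120 over 30 µg in Plain occurs in about 20% to 42%, against about 2.5% under the factorial model. Over SD 0.30 to 0.45 the range is about 10% to 45%. With no dose effect in any family it is only about 3.1%.

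**CD4+ T cells.** The text lets any significant interaction enter, so adjuvant-by-visit may or may not be in the model. The equation's unrestricted mu_jk means it always is. These two statements conflict as well, and the missing significance level leaves the text rule undefined.

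**Templates (section 12.3.2).** The footnote of Template Table 28, which reports D91/D31, lists no visit term. That of Template Table 30 adds gender. Template Table 31 lists Antigen*Adjuvant as its only interaction.

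**The case against.** The strongest objection is that the code already contains what is needed. It is presented as code that will be used, it fits every interaction, and it requests adjuvant-by-visit means sliced by adjuvant, which is the planned second-dose comparison. This stands. A reader might infer from the text alone that the SAP will report identical ratios across adjuvants. The document as a whole does not support that: equality follows only if the text is followed over the code, for the antigen-dose ratios only when the interaction test gives p of 10% or more, and for CD4+ T cells only if adjuvant-by-visit is not retained. What the objection does not remove is the contradiction. The code is also called an example, and nothing ranks it above the text.

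A reader might also take the 20% to 42% as the trial's error rate. It is not. Those rates depend on assumed sample sizes, SDs and effects, with Plain as the only null family. The SAP also makes the superiority t-tests optional, depending on the linear and quadratic dose effects, and section 5.3.1.3 aims the linearity demonstration at the adjuvanted groups.

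Two further points limit the weight. Section 12 says that template footnotes are illustrative and will be adapted, so they are not further binding models. Section 6 calls all comparisons exploratory, and the primary objective is safety. Finally, pre-testing an interaction has defenders, since dropping it narrows intervals. But for a question posed within each family, that narrower interval relies on assuming the families alike.

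**Conclusion.** The contradiction is real and should be fixed. The text and the code of section 5.3.2.3.b specify different mean models for the RSV-group comparisons. Under the text model the three RSV-A second-dose tests are algebraically one test, and that result selects the day for later comparisons. Under the same model the nine antigen-dose ratios reduce to three whenever the interaction is dropped. Under the code neither happens. For CD4+ T cells the inclusion rule has no significance level and conflicts with the equation.

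The equality is algebra and needs no assumptions. The figures of 1.17 for all pools and of 20% to 42% false claims are illustrations under the stated assumed inputs. The exploratory status of the comparisons keeps this below the level of a critical defect.

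**What to change.** - State the code model in the text as the model for RSV-A neutralizing titers: full adjuvant by antigen by visit factorial, baseline, baseline by visit and age category, with unstructured covariance over visits.
- Use the same fixed structure for CD4+ T cells, with the background covariate added.
- Delete both rules that include interactions only if significant. Report the interaction p-values descriptively.
- Align the footnotes and rows of Template Tables 28 to 31 with that model.

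The change is to SAP wording and template footnotes only. Its cost is precision: an estimate from one adjuvant family rather than three uses a third of the data, so within-family intervals can be up to about √3 = 1.73 times as wide as under the main-effects model. That is the appropriate width for a within-family question.
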